5. STUDY POPULATION

The study population will consist of patients with bulbar-onset ALS. A total of 50 patients from France and Italy will be enrolled in the study, primarily through University hospitals setting. A voluntary signed ICF will be obtained from the patients prior to participation in the study.

The recruitment of patients is competitive and will be terminated once the required sample size has been reached.

Patients who meet all the following inclusion criteria and none of the exclusion criteria will be eligible to participate in the study.

5.1 INCLUSION CRITERIA

Patients must satisfy all the following inclusion criteria to be enrolled in the study:

1. Diagnosis of probable or definite ALS according to the revised El Escorial criteria [29], with bulbar onset of disease, familial or sporadic form,
2. Onset of symptoms \leq 18 months prior to screening, as reported by the patient,
3. Adult males or females, aged at least 18 years old,
4. SVC $>$ 60% of predicted value for age and sex,
5. ALSFRS-R score \geq 36,
6. Treatment with riluzole 100 mg/day, at stable dose since at least one month and well tolerated,
7. Male or female patient of childbearing potential¹⁰ who agrees to use highly effective mechanical contraception methods (sexual abstinence, intrauterine device, bilateral tubal occlusion, vasectomised partner) throughout the study, and for 3 months after the end of the treatment,
8. Patient who read, understood and signed the ICF,
9. Patient who is willing to adhere to the study visit schedule and is capable to understand and comply with protocol requirements.

5.2 EXCLUSION CRITERIA

A patient will not be eligible for inclusion in this study if at least one of the following criteria applies:

1. Known other significant neurological disease(s),
2. Serious illness(es) or medical condition(s) (e.g. unstable cardiac disease, cancer, hematologic disease, hepatitis or liver failure, renal failure) that is not stabilised or that could require hospitalisation and may jeopardise the participation in the study,
3. Abnormal renal function at screening defined as estimated glomerular filtration rate (eGFR) $< 60 \text{ mL/min}/1.73\text{m}^2$,

¹⁰ According to the CTFG guideline V2.1 September 2020, a woman is considered of childbearing potential (WOCBP), i.e., fertile, following menarche and until becoming post-menopausal unless permanently sterile. Permanent sterilisation methods include hysterectomy, bilateral salpingectomy and bilateral oophorectomy. A postmenopausal state is defined as no menses for 12 months without an alternative medical cause. A high follicle stimulating hormone (FSH) level in the postmenopausal range may be used to confirm a post-menopausal state in women not using hormonal contraception or hormonal replacement therapy. However, in the absence of 12 months of amenorrhea, a single FSH measurement is insufficient. A man is considered fertile after puberty unless permanently sterile by bilateral orchidectomy.

4. Abnormal liver function at screening defined as total bilirubin levels >1.5 ULN, and/or AST and/or ALT >3 ULN,
5. Neutropenia (ANC $<1.5 \times 10^9/L$) at screening,
6. Other causes of neuromuscular weakness,
7. Non progressive or very rapidly progressing ALS (ALSFRS-R decline from disease onset to randomisation ≤ 0.1 / month or ≥ 1.2 / month)¹¹,
8. Non-invasive ventilation,
9. Tracheotomy,
10. Dementia or other severe active psychiatric illness, including suicidal ideation assessed using the Columbia-Suicide Severity Rating Scale (C-SSRS),
11. Patient with a significant pulmonary disorder not attributed to ALS or who require treatments that might complicate the evaluation of the effect of ALS on respiratory function,
12. Patient treated by edaravone for ALS,
13. Patient using unauthorised concomitant treatments, namely moderate or strong inhibitors or inducers of CYP1A2, strong inhibitors or inducers of CYP2D6 or 2C19 and strong inhibitors of OCT2, as listed in [Section 6.2](#). Combined oral contraceptives containing ethinylestradiol are forbidden concomitant medications,
14. Smoker of > 10 cigarettes per day (e-cigarettes and nicotine patches are permitted),
15. Known hypersensitivity to any of the ingredients or excipients of the IMPs,
16. Pregnant, lactating women,
17. Patient who participated in another trial of investigational drug(s) within 30 days prior to randomisation, or 5 half-lives of the previous investigational product, whichever is longer,
18. Patient who has forfeited their freedom by administrative or legal award, or who is under guardianship or under limited judicial protection.

5.3 WITHDRAWAL OF THE PATIENT

Patients may withdraw from the study at any time without having to provide justification and without penalty to their continuing medical care.

The investigators may withdraw patients from the study for the following reasons:

- Patient withdrawing the consent,
- If, in the investigator's opinion, continuation in the study would be detrimental to the patient's well-being, in particular in case of an AE,
- If, in the investigator's opinion, the patient is unable to maintain the schedule or is non-compliant,

¹¹ Decline will be calculated as follows: 48 minus ALSFRS-R score at the time of inclusion divided by number of months since occurrence of first symptoms of disease, as reported by the patient.

- If the patient becomes pregnant during the study,
- If the patient meets one of the following criteria for permanent drug discontinuation:
 - Increased ALT or AST levels $\geq 5 \times$ ULN.
 - ALT or AST > 3 ULN and total bilirubin levels > 2 ULN.
 - Neutropenia.
 - Symptoms evocative of interstitial lung disease: dry cough and/or dyspnoea, bilateral diffuse lung opacities.
- Lost to FU. A participant will be considered lost to FU if he/she repeatedly fails to return for scheduled visits and is unable to be contacted by the study site. Site personnel are expected to make diligent attempts to contact participants who fail to return for a scheduled visit or are otherwise unable to be followed up by the site.

The date of withdrawal and the principal reason for withdrawal must be recorded in the eCRF and in the patient's records. No additional data will be collected for withdrawn patients. Every effort must be made to contact patients who did not come back for a planned visit/contact.

Every effort will be made to ensure that patients who do not complete all study visits return to the site for the premature discontinuation visit ([Section 4.1.9](#)), as soon as possible and no later than 4 weeks after the last IMP intake. Patients who withdraw due to an AE or SAE will be given appropriate care under medical supervision until the symptoms resolve or the patient's condition becomes stable.

Patients who prematurely withdrew from the study or are lost to FU will not be replaced by new patients.

Any temporary discontinuation of 10 days or less, related to any medical condition that prevents treatment administration based on investigator's judgment, should be allowed and recorded in the eCRF. Any associated AE shall be reported. In case of treatment discontinuation above 10 days, the patient should be withdrawn from the study.

If the participant withdraws consent for disclosure of future information, the sponsor may retain and continue to use any data collected before such a withdrawal of consent. If a participant withdraws from the study, they may request destruction of any samples taken and not tested, and the investigator must document this in the site study records.

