3.5 STUDY COMPLETION AND FOLLOW-UP

A patient is considered to have completed the study if he/she has completed all study visits and attended the V-FU, which must take place 4 weeks (time window \pm one week) after the V4 visit.

The end of the study is defined as the date of the V-FU for the last subject in the study.

All patients who are prematurely withdrawn from the study will undergo a final assessment as soon as possible and no later than 4 weeks after the last study drug intake.

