4.1.8 FU visit – V-FU

The V-FU will occur 4 weeks (\pm 1 week) after V4.

The following assessments will be conducted:

- Physical examination and vital signs assessment, according to [Sections 4.2.1.2](#) and [4.2.1.5](#),
- Weight and calculation of BMI,
- 12-lead ECG ([Section 4.2.1.6](#)),
- Crystalluria analyses according to [Section 4.2.1.9](#),
- Blood and urine samples collection for haematology, blood chemistry, and urinary analysis according to [Section 4.2.1.8](#),
- Serum pregnancy test,

⁸ The sniff test is optional. It will be performed only in sites that have the equipment and resources to perform this test.

- Query for changes in concomitant medications,
- Recording of AEs (if any),
- eCRF recording of data collected.

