4.1.9 Premature discontinuation visit

Patients who prematurely withdraw from the study for any reason (Section 5.3), should be scheduled for a final visit as soon as possible and no later than 4 weeks after the last IMP intake.

The following assessments will be conducted:

- Physical examination and vital signs assessment, according to [Sections 4.2.1.2](#) and [4.2.1.5](#),
- Weight and calculation of BMI,
- 12-lead ECG ([Section 4.2.1.6](#)),
- Blood and urine sample collection for haematology, blood chemistry, and urinary analysis according to [Section 4.2.1.8](#),
- Crystalluria analyses according to [Section 4.2.1.9](#),
- Query for changes in concomitant medications,
- Recording of AEs (if any),
- ALSFRS-R measurement,
- ALS-MITOS measurement,
- King's College score measurement,
- Bioelectrical Impedance Analysis,
- C-SSRS evaluation,
- Patient's completion of ALSAQ-40,
- SVC assessment,
- Urine pregnancy test in WOCBP,
- Sniff test⁹,
- ABG,
- International Normalized Ratio (INR) if CSF sampling is planned,
- Collection of blood, urine and CSF samples for biomarkers analysis according to [Section 4.2.2.3](#),
- eCRF recording of data collected.

⁹ The sniff test is optional. It will be performed only in sites that have the equipment and resources to perform this test.

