7.7 RECORDING OF AN ADVERSE EVENT

The investigator must record all AEs presented or reported by the patient in the AE section of the eCRF. The start date, the actions taken (corrective treatments, dose decrease, temporary or definitive discontinuation of study product, premature withdrawal from the study, none, other) and the outcome (ongoing, recovered with/without sequelae, death) must all be recorded, and the investigator must assess the event in terms of seriousness, severity and relationship to the study products.

When possible, signs and symptoms should be reported as a diagnosis i.e. the investigator should avoid reporting only the signs and symptoms. If there is no medical diagnosis and the signs and symptoms have to be reported, the investigator should record a separate AE for each sign and symptom.

The severity of the AEs will be judged by the investigator(s) and recorded as follows:

- Mild: discomfort noticed but no disruption of normal daily activity,

- Moderate: discomfort sufficient to reduce or affect daily activity,
- Severe: inability to work or perform normal daily activity.

The relationship of the AE to the study product will be judged by the investigator(s) and recorded as follows:

- Not related: a reaction for which sufficient information exists to indicate that the aetiology is unrelated to the study drug; the subject did not receive the study medication or the temporal sequence of the AE onset relative to administration of the study medication is not reasonable or the event is clearly related to other factors (subject's clinical state, therapeutic intervention or concomitant therapy),
- Unlikely: Does not follow a reasonable temporal sequence from administration of the IMP, or is most likely related to another aetiology than the trial drug such as the patient's clinical state, environmental factors or other therapies,
- Possibly: a clinical event, including laboratory test abnormality, with a reasonable time sequence to administration of the drug but which could also be explained by concurrent disease or other drugs or chemicals,
- Probably: a clinical event including laboratory test abnormality, with a reasonable time sequence to administration of the drug, unlikely to be attributed to concurrent disease or other drugs and which follows a clinically reasonable response on withdrawal (de-challenge),

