- Definitely: a reaction that follows a reasonable temporal sequence from administration of the drug, or in which the drug level has been established in body fluids or tissues, that follows a known or expected response pattern to the suspected drug, and that is confirmed by improvement on stopping or reducing the dosage of the drug, and reappearance of the reaction on repeated exposure (re-challenge if applicable).

For safety reporting purpose by the sponsor:

- Reasonable possibility: possibly, probably, definitely related AEs,
- No reasonable possibility: not related, unlikely related AEs.

All AEs and SAEs will be collected from the time of signing of the ICF until participation in study has ended. There is no time limit for investigators for reporting to the sponsor related SAEs they are made aware of.

Adverse events that begin before the start of study intervention but after signing of the ICF will be recorded on the AE eCRF (NTEAEs).

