5.2.15 Treatment emergent adverse event

TEAE is defined as an adverse event occurring (or existing symptoms worsened) on or after the day of first dose intake of study product and up to study end.

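### Off-drug safety follow-up is 21–35 days for completers but one visit at 0–28 days for patients who stop early, so adverse-event ascertainment is unequal if drop-out differs by arm

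*Protocol*

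**What the plan says.** **Completers.** Protocol 4.1.8: "The V-FU will occur 4 weeks" (± 1 week) after V4. The visit covers adverse events, blood and urine safety tests, ECG and crystalluria. Sections 3.1 and 3.5 also define it only relative to V4.

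**Patients who stop early.** Protocol 5.3: "In case of treatment discontinuation above 10 days, the patient should be withdrawn from the study". Under Protocol 4.1.9, patients who withdraw "should be scheduled for a final visit as soon as possible and no later than 4 weeks after the last IMP intake". Section 4.2.1.9 places the second crystalluria test at the follow-up visit or at the discontinuation visit, so one stands in for the other. Section 5.3 adds: "No additional data will be collected for withdrawn patients". Since the same section asks for the discontinuation visit, the sensible reading is that collection closes after that visit.

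**What is counted.** Protocol 7.7: "All AEs and SAEs will be collected from the time of signing of the ICF until participation in study has ended". SAP 5.2.15 counts as treatment-emergent any event "on or after the day of first dose intake of study product and up to study end". SAP 5.12.1 reports numbers of events and numbers and percentages of patients, without adjustment for length of observation.

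**Last intake.** Protocol 6.1.2 has the date of last intake documented in the eCRF. SAP 5.2.10 does not use it. It takes the V4 date for patients who completed treatment and the end-of-study date for those who discontinued.

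**The concern.** The primary endpoint (Protocol 2) is the incidence, grade and relationship of TEAEs, SAEs and AESIs, plus events leading to interruption or discontinuation. Every completer is seen at a set interval off drug. A patient who stops early has no such guaranteed interval, and routine collection then ends even if the patient would agree to stay in contact.

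If drop-out is the same in both arms, each arm loses the same fraction of off-drug observation. If it differs, the crude TEAE percentages compare arms watched for different lengths of time. Because of the last-intake derivation in SAP 5.2.10, the report would not show this.

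**Working it through.** **1. The plan's own figures.** With 28 patients on IFB-088 (Protocol 8.1.2), P(at least one SAE) = 1 − (1 − p)^28.
- p = 5%: 1 − 0.95^28 = 0.762. p = 10%: 1 − 0.90^28 = 0.948. Both match the plan.
- 42 / 0.85 = 49.4, rounded up to 50. This also matches.

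**2. Off-drug windows.**

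| | Earliest last safety visit | Latest |
|---|---|---|
| Completer, days after V4 | 28 − 7 = 21 | 28 + 7 = 35 |
| Early leaver, days after last intake | 0 | 28 |

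The ranges overlap from day 21 to day 28. The guaranteed minimum is 21 days for completers and 0 for leavers. A patient withdrawn because an interruption passed 10 days is already more than 10 days off drug, so a visit after that withdrawal falls after day 10.

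**3. Washout.** Half-life after multiple dosing is 5.7 to 8.4 h (Protocol 1.1.2.2). Five half-lives are 5 × 5.7 = 28.5 h to 5 × 8.4 = 42 h. A visit on the day of stopping precedes washout; a visit after a ten-day interruption does not.

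**4. Patients concerned.** 50 × 0.15 = 7.5, so 7 or 8 overall. With 2:1 allocation, 50 × 2/3 ≈ 33 on IFB-088 and 17 on placebo. 33 × 0.15 ≈ 5 on IFB-088.

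**5. Off-drug time at stake, at most 4 weeks per leaver.** If everyone had 4 weeks, the totals would be 33 × 4 = 132 patient-weeks on IFB-088 and 17 × 4 = 68 on placebo.
- Equal 15% drop-out: up to 15% is lost in each arm (5 × 4 = 20 of 132 on IFB-088), with no difference between arms.
- Extreme case, assumed for illustration: all 8 leavers on IFB-088. Up to 8 × 4 = 32 of 132 (24%) is lost there and none on placebo. Against a full schedule of 33 × 30 = 990 patient-weeks (26 weeks of treatment plus 4), that is about 3%.

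**6. Effect on SAE detection.** With all 33 observed, the probabilities would be 1 − 0.95^33 = 81.6% and 1 − 0.90^33 = 96.9%. The stated 76.2% and 94.8% are what remains if the 5 leavers contribute nothing (33 − 5 = 28). Assuming constant risk over 30 weeks and 4 full weeks lost per leaver, the expected SAEs missed are 5 × 0.05 × 4/30 = 0.03, or 5 × 0.10 × 4/30 = 0.07.

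**7. What the SAP would show.** For a discontinued patient, end of study minus derived last intake is always 0 days, whatever the true gap. An event up to 28 days off drug would be dated as on treatment.

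**The case against.** The case against a serious gap is strong in several places, and most of it stands.

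- **The discontinuation visit is a full safety visit.** Protocol 4.1.9 and Table 3 include creatinine, eGFR, urinalysis, crystalluria, ECG and adverse events. A reader might infer that the kidney goes unchecked after stopping; the documents do not support that. What is missing is a guaranteed interval off drug.
- **Important events keep their own channels.** Protocol 7.7 sets no time limit on reporting related SAEs. Sections 7.8 and 7.9 require SAE and AESI follow-up information, and renal toxicities are AESIs. The event that causes stopping is itself in the primary endpoint. So one cannot read the plan as collecting nothing on patients who stop for toxicity.
- **The visit need not fall at day 0.** Nothing documents when it happens in practice, and the ten-day route in Protocol 5.3 puts it later.
- **Relationship grading.** Under Protocol 7.7, a probable relationship is one "which follows a clinically reasonable response on withdrawal (de-challenge"), which a same-day visit cannot show. One might infer that related-event counts are therefore biased. But SAP 5.2.16 counts everything from unlikely to definitely, and missing, as related, so a shift between those grades changes no summary count.
- **Direction.** That the arm with more leavers would look safer is possible but not shown. Discontinuations due to adverse events are tabulated, and lost on-treatment time is inherent in stopping.

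What survives is narrower. After the discontinuation visit there is no provision for new non-serious, non-AESI events and their outcomes, for SAEs and deaths judged unrelated (Protocol 7.8 limits later SAE reports to those thought caused by the product or a procedure), or for laboratory tests at a set time off drug. Completers have all of these through day 21 at least.

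**Conclusion.** The concern holds in limited form. Off-drug ascertainment for the primary endpoint is unequal by design: at least 21 days for completers and possibly none for early leavers. The SAP derivation conceals it. It concerns 7 or 8 patients, about 5 on IFB-088, if the planned 15% drop-out and 2:1 split hold. It distorts the comparison between arms only if drop-out differs between them.

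The size is modest. At most 4 weeks per leaver is at stake, few SAEs would be expected in that time, and the sample-size statement is unaffected. The number of non-serious events missed cannot be derived from the documents, which give no such rate.

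Protocol 5.3 also conflicts with other sections. Section 3.9.1.1 encourages scheduled visits after emergency unblinding, although the product is stopped for good. Sections 7.7 and 7.8 keep some reporting open after the last visit. These must be reconciled. The remedy is cheap enough that the change should be made.

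**What to change.** 1. **Protocol 4.1.8, 4.1.9 and 5.3.** Tie the safety follow-up contact to the last intake for every patient who still consents. Use the existing visit, or a phone contact for adverse events, their outcome and vital status, with the local creatinine prescription the trial already uses. Limit the no-further-data sentence to withdrawal of consent to further data. Reconcile 5.3 with 3.9.1.1, 7.7 and 7.8.
2. **SAP 5.2.10.** Use the date of last intake recorded in the eCRF.
3. **SAP 5.2.15.** Count TEAEs from first dose to last intake plus a fixed number of days that the contact covers for everyone. The cut-off must fit the visit window: 28 days needs a contact no earlier than day 28, while the present ± 1 week window supports 21 days. Tabulate on-treatment and post-treatment events separately by arm.
4. **If the protocol change is too late.** The synopsis plans last patient out in the third quarter of 2024, and the SAP is dated November 2024. In that case make the SAP changes before unblinding, and report the length of off-drug follow-up by arm as a limitation. A common window cannot recover events that were never collected.

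The cost is one existing visit or a phone call for about 7 or 8 patients, some SAP wording and one extra table split. Some leavers will decline.

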6. STUDY PRODUCTS

The study product is defined as “a pharmaceutical form of an active substance or placebo being tested or used as a reference in a clinical study, including products already with a marketing authorisation but used or assembled (formulated or packaged) in a way different from the authorised form, or when used for an unauthorised indication, or when used to gain further information about the authorised form”. In this trial, the study products are IFB-088 and its matching placebo.

IFB-088 and placebo will be provided as white, oblong, immediate release 200 mg tablets, with the same composition except for the active ingredient, i.e. 25mg of IFB-088 per tablet for the IFB-088 tablets.

IFB-088 and placebo tablets excipients are listed in [Table 4](#).

Table 4 - Composition of IFB-088 and placebo tablets

Compound	Function
IFB-088 acetate salt	Active pharmaceutical ingredient
Microcrystalline cellulose	Filler
Silica, colloidal hydrated	Glidant
Crospovidone	Disintegrant
Magnesium stearate	Lubricant

6.1 INVESTIGATIONAL MEDICINAL PRODUCTS

6.1.1 Dosage and dosage schedule of the investigational medicinal products

The test product, IFB-088, will be administered in 50 mg/day dosage consisting of two uptakes of 25 mg each, as an add-on therapy to riluzole 100 mg. The placebo will be administered in two uptakes, as an add-on therapy to riluzole 100 mg.

Administration of riluzole 100 mg, tablet or suspension, will be at the patient's and/or investigator's choice, as per summary of product characteristics [44]. The daily dose of 100 mg will be taken in two 50 mg doses every 12 hours, at the same time than the IMPs.

